#### Definitions:

- normal thyroid function: serum TSH and free T4 within normal limits;
- primary hypothyroidism: serum TSH >ULN and free T4 <LLN;
- secondary hypothyroidism: serum TSH <ULN and free T4 <LLN;
- subclinical hypothyroidism: TSH >ULN and a free T4 within normal limits.

TPO antibodies will be measured in patients with elevated TSH levels to determine the status of thyroid autoimmunity.

Frequency of newly occurring hypothyroidism and shift tables will be provided for each treatment group. Results will also be shown separately for each year since randomization.

#### Proportion of patients with worsening of glucose metabolism

An annual oral glucose tolerance test will be carried out to evaluate changes of glucose metabolism compared to the baseline status. The proportion of patients with an increase in glucose metabolism category (normal, impaired glucose metabolism, diabetes mellitus) based on the American Diabetes Association criteria (American Diabetes Association 2009) compared to their baseline result will be determined at each timepoint, i.e. 1, 2, years after randomization. For this classification, fasting and 2-hour post-prandial plasma glucose levels will be measured.

#### Criteria for impaired glucose metabolism:

• fasting plasma glucose (FPG) levels ≥ 100 mg/dl (5.6 mmol/L) but <126 mg/dl (7.0 mmol/L)

#### OR

• 2-h values in the oral glucose tolerance test (OGTT) of  $\geq$  140 mg/dl (7.8 mmol/L) but  $\leq$ 200 mg/dl (11.1 mmol/L).

#### Criteria for diabetes mellitus:

symptoms of diabetes plus casual plasma glucose concentration ≥ 200 mg/dl
 (11.1 mmol/L) Casual is defined as any time of day without regard to time since last meal.

 The classic symptoms of diabetes include polyuria, polydipsia, and unexplained weight loss.

#### OR

- FPG ≥ 126 mg/dl (7.0 mmol/L). Fasting is defined as no caloric intake for at least 8 hours. **OR**
- 2 hour postload glucose ≥ 200 mg/dl (11.1 mmol/L) during an OGTT. The test should be performed as described by WHO, using a glucose load containing the equivalent of 75 g anhydrous glucose dissolved in water.

Frequency and shift tables will be provided for each treatment group. Results will also be shown separately for each year since randomization.

## Disease progression

An evaluation of the time from randomization to either MDS progression or progression to AML in the treatment groups will be done based on date of diagnosis of MDS progression or date of first diagnosis of AML minus date of randomization plus 1.

MDS progression will be defined as a transition into a higher MDS risk group based on IPSS scoring. Progression to AML will be defined based upon the most current classification guidelines (Vardiman 2009), as 20% or more blasts seen in the bone marrow collected by biopsy or aspirate.

The time-to-event analysis follows the description given in Section 10.4.2.1 to Section 10.4.2.4. Censoring for patients with neither MDS progression nor progression to AML at the time of a data cut-off is described in Section 10.4.3. Further details will be described in the RAP.

#### Time to first occurrence of serum ferritin > 2 times the baseline value

An evaluation of the time from randomization to the first occurrence of serum ferritin > 2 times the baseline value at two consecutive assessments (at least two weeks apart) will be performed per treatment group based on the following variable:

date of the first of the two consecutive laboratory assessment fulfilling the criterion of SF
 2 × baseline value minus date of randomization plus 1.

The time-to-event analysis follows the description given in Section 10.4.2.1 to Section 10.4.2.4. Censoring for patients without such a serum ferritin increase at the time of a data cut-off is described in Section 10.4.3.

#### Time to at least a 10% increase from baseline in LVIDD

An evaluation of the time from randomization to the first occurrence of an increase of at least 10% from the baseline value of LVIDD will be performed based on the following variable:

• date of echocardiography assessment where a minimum of 10% increase first occurred minus date of randomization plus 1.

The time-to-event analysis follows the description given in Section 10.4.2.1 to Section 10.4.2.4. Censoring for patients without such an increase in LVIDD at the time of a data cut-off is described in Section 10.4.3. If necessary, further details will be described in the RAP.

#### Time to at least a 10% increase from baseline in LVISD

An evaluation of the time from randomization to the first occurrence of an increase of at least 10% from the baseline value of LVISD will be performed based on the following variable:

• date of echocardiography assessment where a minimum of 10% increase first occurred minus date of randomization plus 1.

The time-to-event analysis follows the description given in Section 10.4.2.1 to Section 10.4.2.4. Censoring for patients without such an increase in LVISD at the time of a data cut-off is described in Section 10.4.3. If necessary, further details will be described in the RAP.

#### Infections

Infections requiring intravenous antimicrobials during the treatment period (until the 28 day follow-up visit) will be evaluated separately for each treatment group.

#### **Definitions:**

- Infections will be determined from the reported adverse events with system organ class "Infections and infestations" and action taken "Concomitant medication taken".
- Antimicrobial therapy will be determined from the reported concomitant medications for patients who had an infection AE. The selection of medications will be based on a prespecified list of WHO low level ATC codes. The route of administration needs to be specified as "intravenous (i.v.)".
- Contemplable events will be combined with medications (of the same patient) based on the following criterion: start date of medication ≥ start date of AE and start date of medication ≤ minimum (start date of AE + 1, end date of AE).

The total number of infections will be counted and summarized per treatment group. For this number one patient can contribute more than one infection event. To account for different lengths of observation time in the two groups, the rate of infections will be calculated with the number of recorded infections treated with intravenous antimicrobials divided by the total number of patient-years of follow-up. The relative risk of infection will be calculated as the rate of infection in the treatment group compared with the rate in the placebo group.

## 10.5.2 Secondary safety objectives

#### 10.5.2.1 Observation periods for safety

The overall observation period will be divided into three mutually exclusive segments:

- 1. Pre-treatment period: from day of patient's informed consent to the day before first dose of study medication.
- 2. On-treatment period: from day of first dose of study medication to 28 days after last dose of study medication.
- 3. Post-treatment period: starting at day 29 after last dose of study medication.

Safety summaries (tables and figures) have to include only data from the pre-treatment period (to display "baseline status") and the on-treatment period, i.e. no data from the post-treatment period are to be included. In particular, summary tables for adverse events (AEs) will include only AEs that occurred or worsened during the on-treatment period, the so-called **treatment-emergent** AEs.

However, all safety data (including those from the post-treatment period) will be listed and those collected during the pre-treatment and post-treatment periods will be flagged.

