## Patients meeting a non-fatal component of the composite primary endpoint

The end of study treatment will occur if a patient meets any non-fatal component of the composite primary endpoint (Section 3.1.1) confirmed by the Endpoint Adjudication Committee (EAC). His/her individual randomized study treatment will be unblinded and discontinued at that time. The subsequent iron chelation treatment is subject to the patient's

and the investigator's decision. After termination of study treatment, all patients will continue to be followed for safety and non-fatal components of the primary endpoint during the evaluation period at visits occurring every three months. Subsequent to the evaluation period, or at the end of treatment if a patient and treating physician decide that a patient will not participate in the evaluation period, patients will be followed every 6 months for iron chelation therapies and overall survival ("Survival Follow-up").

All suspected endpoint events will be reviewed and adjudicated by the EAC; however, only the first confirmed endpoint for a patient will be counted for the composite primary endpoint. The role of the EAC is to ensure that all events that have been reported are judged uniformly using the same criteria. The EAC is blinded to study treatment.

[figure not shown]

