#### 6.7.4 Other concomitant medications

The investigator should instruct the patient to notify the study site about any new medications he/she takes after the start of the study drug. All medications (other than study drug) and significant non-drug therapies (including physical therapy and blood transfusions) administered after the patient starts treatment with study drug must be listed on the appropriate eCRF page.

The treatment of concomitant medical conditions with non-investigational medications during the study may be continued with the exception of other chelating agents.

The following concomitant medications may be permitted for use while patient is on study and information outlining start date(s) and end date(s) of each medication taken must be recorded on the appropriate eCRF:

- Erythropoietin (growth factor)
- G-CSF (growth factor)
- GM-CSF (growth factor)
- Azacitidine
- Thalidomide
- Arsenic trioxide
- Lenalidomide
- Decitabine
- Cyclosporine A
- Vitamin C supplements (≤ 200 mg/day)

Any investigational drug other than study medication is NOT allowed during the study. After permanent discontinuation of the randomized study medication, the use of commercially available iron chelation therapies is allowed.

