2.1.2.9 On-treatment assessment/event and observation periods

The overall observation period will be divided into three mutually exclusive segments:

- 1. *pre-treatment period*: before the first administration of study treatment
- 2. *on-treatment period*: from date of first administration of study treatment to 28 days after date of last actual administration of any study treatment (including start and stop date)
- 3. *post-treatment period*: starts on day 28+1 after last administration of study treatment.

Per study design, there will be two additional observation periods:

- 4. *study evaluation period:* starts on day 29 after last administration of study treatment until study evaluation completion period (visit frequency every three months)
- 5. **survival follow-up period:** starts after study evaluation completion visit until LPFV plus three years or death. If a patient declines to participate in the evaluation period, the survival follow-up period will start on day 29 after last administration of study treatment until LPFV plus three years or death (visit frequency is every 6 months).

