2.4.5.2 Chelation therapy after discontinuation of study treatment

The number of patients chelated since discontinuation of study drug will be summarized and categorized as reported within 28 days since discontinuation or later. In the summary table, deferoxamine mesilate will be displayed as "deferoxamine".

Chelation therapy after discontinuation of study treatment will be listed using the FAS.

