2.8.1 Adverse events (AEs)

All AEs recorded during the study are coded using the latest version of the medical dictionary for regulatory activities (MedDRA) and summarized by treatment group and overall. Adverse events are not assessed according to the common terminology criteria for AEs (CTCAE); instead, AE severity (mild, moderate, severe) is used to report treatment-emergent AEs starting on or after the date of first study medication (including AEs that start within 28 days after the discontinuation of the study medication).

Frequency tables for treatment-emergent AEs will be presented, for each treatment group, the number of patients, and the percentage of patients experiencing the AE. Multiple occurrences of the same event in the same patient will be counted only once in the frequency tables. However, all adverse events will be included in the AE listings.

Frequency tables will display at least the MedDRA system organ class and preferred term, AE severity (mild, moderate, severe), and relationship to study drug. The following tables will be generated:

• Adverse events, regardless of study drug relationship

- Serious adverse events, regardless of study drug relationship
- Serious adverse events, suspected to be study drug relationship
- Adverse events leading to study drug discontinuation, regardless of study drug relationship
- Adverse events requiring dose adjustment or interruption, regardless of study drug relationship
- Adverse events requiring additional therapy, regardless of study drug relationship
- Adverse events, suspected to be study drug related
- Adverse events which are not serious adverse events, regardless of study drug relationship

For the requirements of ClinicalTrials.gov and EudraCT, two required tables on <ontreatment/treatment emergent> adverse events which are not serious adverse events with an incidence greater than 5% and on <on-treatment/treatment emergent> serious adverse events and SAE suspected to be related to study treatment will be provided by system organ class and preferred term on the safety set population.

If for a same patient, several consecutive AEs (irrespective of study treatment causality, seriousness and severity) occurred with the same SOC and PT:

- a single occurrence will be counted if there is ≤ 1 day gap between the end date of the preceding AE and the start date of the consecutive AE

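### The 28-day safety tail is not cut when a patient starts a commercial chelator, so adverse events in placebo patients who move to commercial deferasirox are tabulated under placebo; the bias is probably small but easy to check

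*Protocol*

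**What the plan says.** The protocol (10.5.2.1) defines the window for safety summaries as "On-treatment period: from day of first dose of study medication to 28 days after last dose of study medication". Of what lies beyond it, the protocol says that "no data from the post-treatment period are to be included". SAP 2.1.2.9 has the same limits: "from date of first administration of study treatment to 28 days after date of last actual administration of any study treatment". SAP 2.8.1 defines treatment-emergent adverse events to match, "including AEs that start within 28 days after the discontinuation of the study medication". Both documents (Protocol 10.1, SAP 2.2.3) analyse each patient for safety under the study medication given first, so a later switch does not change the arm.

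On chelation after study drug, Protocol 6.7.4 states: "After permanent discontinuation of the randomized study medication, the use of commercially available iron chelation therapies is allowed". No waiting period is given, and Protocol 10.4.3 makes clear that marketed therapy includes Exjade. For a patient with an adjudicated non-fatal endpoint, Protocol section 4 adds: "His/her individual randomized study treatment will be unblinded and discontinued at that time". What chelation follows is left to the patient and the investigator.

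The SAP provides for chelation inside the tail. Section 2.4.5.2 counts patients chelated after stopping, "categorized as reported within 28 days since discontinuation or later". For event-free survival, SAP 2.5.4 includes a sensitivity analysis censored at the first subsequent chelator, and SAP 5.5.4 allows optional IPCW or RPSFT analyses. SAP 2.8 and its subsections contain nothing comparable for safety.

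**The concern.** Take a patient who stops placebo, starts commercial deferasirox a few days later and has an adverse event on day 10 after the last placebo dose. Under both definitions this is a placebo treatment-emergent event.

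The protocol synopsis says that the safety analysis is meant to exclude levels of increased risk that would be clinically unacceptable, using 95% confidence intervals for risk ratios. For an event that deferasirox increases, deferasirox-exposed cases in the placebo numerator lower the estimated ratio and make an unacceptable risk easier to exclude. The days concerned are also the first days on the drug. Protocol 6.7.1.9 places most serious hypersensitivity reactions in the first month of treatment.

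The plan handles switching for efficacy and gives no reason for leaving safety out.

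**Working it through.** The plan has no figure to reproduce here. The sample size rests on feasibility, and no safety risk or switching rate is stated. The check has two parts.

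**1. Is there any truncation?** The window definitions (Protocol 10.5.2.1, SAP 2.1.2.9) and the safety sections (Protocol 10.5.2.2 to 10.5.3, SAP 2.8 to 2.8.4.3) contain no rule that ends, flags or repeats an analysis at the start of a non-study chelator. Protocol 6.6.1.4 bars other chelation during study treatment, so the overlap can lie only in the 28-day tail.

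**2. How large could the effect be?** Inputs:

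- Arms: 210 patients at 2:1, so 140 on deferasirox and 70 on placebo.
- Deferasirox risk p1 = 26%, the first-year rate of GI disturbance in Protocol 1.3. It serves only as an illustration; it is not one of the pre-specified safety endpoints.
- Placebo risk p0 = 10%: assumption. True risk ratio = 0.26 / 0.10 = 2.60.
- s = share of placebo patients who start commercial deferasirox in the tail: assumption, 10% to 50%.
- x = risk of the event over 28 days on commercial deferasirox, each switcher being taken as exposed for all 28 days. This overstates x for anyone who starts later.

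Three values of x, according to when the 26% arises:

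- constant hazard over the year: 1 − 0.74^(28/365.25) = 2.3%
- all risk within 90 days: 1 − 0.74^(28/90) = 8.9%
- all risk within 28 days: 26%, an upper bound

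Tabulated placebo risk = p0 + s × (1 − p0) × x, with deferasirox held at 26%. For s = 30% and constant hazard this is 0.10 + 0.30 × 0.90 × 0.0228 = 0.1062, and 0.26 / 0.1062 = 2.45. Expected switchers with the event in the tail = 70 × s × x, here 70 × 0.30 × 0.0228 = 0.48.

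Reported risk ratio, with expected switchers having the event in brackets:

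| Timing of risk | s = 10% (7 switchers) | s = 30% (21) | s = 50% (35) |
|---|---|---|---|
| Constant hazard | 2.55 (0.16) | 2.45 (0.48) | 2.36 (0.80) |
| All within 90 days | 2.41 (0.63) | 2.09 (1.88) | 1.85 (3.13) |
| All within 28 days | 2.11 (1.82) | 1.53 (5.46) | 1.20 (9.10) |

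The tail is a small part of the window: 28 / (365.25 + 28) = 7.1% for a patient with one year of exposure, and 28 / (1095.75 + 28) = 2.5% with three years.

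**Which outputs are exposed.** AE-based outputs are the main ones: the AE and SAE tables, adverse events of special interest, major GI bleeding and on-treatment deaths. Tables limited to events suspected to be drug-related may be partly protected by the investigator's causality judgement. Laboratory endpoints are little exposed. The 28-day visit in Table 7-1 schedules only adverse events and chelation, and renal dysfunction needs two creatinine values at least 7 days apart. Toxicity follow-up under Protocol 6.7.2 and unscheduled tests can still add some values. Time to discontinuation due to an adverse event is fixed when study drug stops, so it is not affected.

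**The case against.** The strongest case against has four parts.

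- **The tail has a purpose.** It captures delayed effects of study drug and matches the 28-day AE follow-up in Protocol 6.7.5. Cutting it at a new chelator is informative: a deferasirox patient who stops for toxicity and changes chelator would lose late study-drug events, which also understates harm. This stands, and is why the protocol window should remain primary.
- **The rate and direction are uncertain.** Planned unblinding applies only after an adjudicated non-fatal event, and the 28-day category in SAP 2.4.5.2 is descriptive, so it is not evidence that early switching is common. Deferasirox patients may also take a commercial chelator in the tail, which may not be deferasirox, and this can add to their numerator too. This stands: the calculation above holds the deferasirox arm fixed.
- **The overlap can already be seen.** Chelation and all adverse events are listed, and the safety analyses are exploratory. This holds in part. A reader could match the listings by hand, but no risk ratio without the overlap would be produced.
- **IV infections are an efficacy endpoint.** Protocol section 10.5.1.1 and SAP 2.7.1.8 use the same 28-day limit, so the window is contaminated there too. The rationale given for that endpoint is that chelation may reduce infections, so dilution could hide a benefit instead of a harm.

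A reader might infer that every safety risk ratio in the trial is materially diluted, or that the window itself should be replaced. The documents support neither. Large dilution needs both frequent early switching, which they do not document, and first-year risk packed into a few weeks.

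**Conclusion.** The gap is real and follows from the text of both documents: adverse events in placebo patients who start commercial deferasirox within 28 days of the last dose are tabulated as placebo events. For AE-based outputs and events that deferasirox increases, excess switching on placebo biases the risk ratio toward 1, against the stated safety aim.

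The effect is probably small. Under constant hazard, 2.60 becomes 2.55 to 2.45 at 10% to 30% switching. It reaches 2.09 at 30% if all the risk falls within 90 days, and 1.53 only in the extreme 28-day case. These figures rest on the assumed switching share, the assumed 10% placebo risk, full 28-day exposure for every switcher, no added events in the deferasirox arm, and GI disturbance as the example. With about 70 placebo patients, even two or three such cases could matter for a rare event such as major GI bleeding.

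This justifies a supplementary analysis. It does not justify a change to the primary definition.

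**What to change.** Keep the protocol window as primary. Add to SAP 2.8 and 2.7.1.8 a pre-specified sensitivity analysis of the AE overview, SAEs, adverse events of special interest, major GI bleeding and IV infections. In it, the on-treatment period ends at the earlier of 28 days after the last dose and the day before the first post-study chelator. For the infection rate, cut the patient-years at the same date. In the listings, flag events that start on or after the first post-study chelator.

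The dates come from the existing eCRF on chelation after study drug (Protocol 6.7.5), and SAP 5.1.3.2 already has a rule for partial start dates. In the truncated version, events misattributed through switching fall to zero by construction.

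The cost is one derived date, SAP wording and a few extra tables, with no new data. The truncated version may drop some delayed study-drug effects, so it should be read beside the primary window and not in place of it.

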### 10.5.2.2 Secondary safety variables and related analyses

Analyses of safety endpoints related to secondary objectives of the trial will be analyzed for the safety analysis set. Descriptive statistics and two-sided 95% confidence intervals (without adjustment for multiplicity) for evaluation of deferasirox in contrast to placebo will be used as appropriate.

### Proportion of patients with significant renal dysfunction

Treatment groups will be evaluated regarding the proportion of patients experiencing a significant renal dysfunction. This is defined as a serum creatinine value  $\geq 2$  times ULN at two consecutive assessments. The two assessments need to be at least 7 days a part.

Frequency tables by treatment group will be prepared. Results will also be provided for annual time intervals.

